When estimating incidence rates we will assume a minimum lag time of 6 months between the start of treatment and the occurrence of the study endpoints. This implies that person-time for the interval of the first 6 months since start of treatment will be excluded, along with any events that occur within this time period. This lag time encompasses a period of drug utilization and dose accumulation, a period of induction time (from causal action of exposure to disease initiation), and a latency period (from disease initiation to disease detection). The induction time for the occurrence of skin cancer and lymphomas associated with the use of tacrolimus and pimecrolimus is unknown. Therefore, we will conduct sensitivity analyses to estimate incidence rates within the first 6 months of treatment and for several lag times longer than the initial 6 months. The lag time analysis will also be used to explore potential protopathic bias if early symptoms of skin cancer or lymphoma are erroneously treated as atopic dermatitis and therefore the reason for starting treatment.

The goal of the first secondary objective is to obtain background rates among persons not treated with the study medications and to put in perspective potential differences among the untreated population, the atopic dermatitis cohort treated with moderate- to high-potency corticosteroids (see Section 9.3.1, Identification of Atopic Dermatitis, for further details on atopic dermatitis criteria), and the tacrolimus cohort.

9 Research Methods

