9.3.4 Exposure Assessment

To assess the effect of exposure to topical tacrolimus and topical pimecrolimus, we assume that exposure to either of the two medications results in a lifetime change in risk for the effects of that specific medication. That is, if a patient is exposed to topical tacrolimus (tacrolimus cohort), the status of exposure to tacrolimus is maintained throughout follow-up even after stopping therapy with tacrolimus. However, time at risk will start after the lag time of 6 months is completed.

Accordingly, person-time of follow-up of each cohort (topical tacrolimus and topical pimecrolimus) will be classified in several categories of exposure.

[figure not shown]

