9.3.4.1 Exposure to Topical Tacrolimus

- *Ever use of topical tacrolimus:* person-time starting 6 months after the date of the first prescription for topical tacrolimus to the end of follow-up (Figure 4). In this exposure category, any potential switching to topical pimecrolimus is ignored (all person-time of follow-up is allocated to topical tacrolimus).

In addition, the overall person-time of follow-up of topical tacrolimus will be classified in two mutually exclusive categories (Figure 4):

- *Single use of topical tacrolimus (monotherapy with topical tacrolimus):* person-time starting 6 months after the date of the first prescription for topical tacrolimus to the earliest of the following dates: 6 months after the date of receiving a prescription for topical pimecrolimus or date of end of follow-up.
- *Switching (from topical tacrolimus to topical pimecrolimus)/multiple use:* person-time starting 6 months after the date of receiving a prescription for topical pimecrolimus to the end of follow-up.

Figure 4. Exposure Assessment: Example for Exposure to Topical Tacrolimus

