9.3.4.2 Exposure to Topical Pimecrolimus

The same exposure rationale described for topical tacrolimus will be implemented for defining exposure to topical pimecrolimus, with pimecrolimus as the first exposure and tacrolimus as the second or additional exposure.

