9.3.4.6 Cohort of Users of Corticosteroids

Person-time will be accumulated from the date of cohort entry to the earliest of the following dates: prescription for topical tacrolimus, prescription for topical pimecrolimus, or end of follow-up (Figure 5).

[figure not shown]
Figure 5. Exposure Assessment: Example for Patients Contributing Person-time to Both the Corticosteroids Cohort and the Tacrolimus Cohort

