9.3.4.7 Untreated Cohort

Person-time will be accumulated from the start date (see Section 9.2.3.3) to the earliest of the following dates: prescription for moderate- to high-potency topical corticosteroids, prescription for topical tacrolimus, prescription for topical pimecrolimus, or end of follow-up (Figure 6).

Figure 6. Exposure Assessment: Example for Patients Contributing Person-time to the Untreated Cohort and Any Other Cohort

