9.7.2.5 Sensitivity Analysis

Sensitivity analyses will be conducted for single use of topical tacrolimus and topical pimecrolimus. The following sensitivity analyses will be conducted:

1. Incidence rates and incidence rate ratios will be estimated for the subgroup of children aged ≥ 2 to < 16 years, which is the age range for children specified in the labeling of topical tacrolimus.
2. Incidence rates and incidence rate ratios will be estimated for the occurrence of each specific endpoint regardless of a prior occurrence of any of the other study endpoints during the study period.
3. Incidence rates and incidence rate ratios will be estimated for the occurrence of all MMs and NMSCs excluding in situ carcinomas, to evaluate the role, if any, of the inclusion of noninvasive skin carcinomas.
4. Incidence rates and incidence rate ratios will be estimated for basal cell carcinoma and squamous cell carcinoma separately.
5. Incidence rates and incidence rate ratios will be estimated for cutaneous and noncutaneous lymphomas separately.
6. Incidence rates and incidence rate ratios will be estimated by strata of propensity scores to explore effect modification.
7. To evaluate protopathic bias, incidence rates and incidence rate ratios will be estimated for the first 6 months after the first exposure (ignoring lag time), and for other lag times (e.g., 12 months, 18 months, 24 months, 48 months) in addition to the predefined lag time of 6 months.
8. To explore potential surveillance bias, incidence rates of malignant melanoma and non-melanoma skin cancer will be stratified by stage of malignancy at the time of diagnosis in those data sources where information on stage is available. Data on stage of cancer at diagnosis can be useful to assess the potential role of a higher medical surveillance in the detection of cases (if lower stages are found, higher medical surveillance is likely to have occurred).
9. Incidence rates and incidence rate ratios will be estimated by severity of atopic dermatitis. In Phase I, definition of severity of atopic dermatitis was based on the utilization of health care resources. However, information was only partially available in the study data sources. In the JOELLE Extension, severity of atopic dermatitis will be defined according to the type of prescriber of the first prescription (dermatologist or nondermatologist) as a proxy for severity.

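### Section 9.3.4.6 starts corticosteroid person-time at cohort entry, in conflict with the general 6-month lag in Section 8; if programmed as written, only the exposed side of the primary rate ratio is lagged

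*Protocol*

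**What the plan says.** **Exposed cohorts.** Section 9.3.4 introduces the lag for two cohorts by name: "person-time of follow-up of each cohort (topical tacrolimus and topical pimecrolimus) will be classified in several categories of exposure". Section 9.3.4.1 defines ever use as "person-time starting 6 months after the date of the first prescription for topical tacrolimus to the end of follow-up". Section 9.3.4.2 carries this over: "The same exposure rationale described for topical tacrolimus will be implemented for defining exposure to topical pimecrolimus". Section 9.3.4.4 repeats the 6-month induction period for each level of cumulative dose, the main exposure measure.

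**Comparator.** Section 9.3.4.6 is the only rule that defines corticosteroid person-time: "Person-time will be accumulated from the date of cohort entry to the earliest of the following dates". The end dates listed are a tacrolimus prescription, a pimecrolimus prescription or the end of follow-up. No lag appears. Section 9.3.4.7 treats the untreated cohort in the same way: "Person-time will be accumulated from the start date".

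**General statement.** Section 8, on estimating incidence rates, says that "person-time for the interval of the first 6 months since start of treatment will be excluded, along with any events" in that window. It does not say which cohorts it covers.

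**Use.** Section 9.7.2.3 takes the rate in the corresponding corticosteroid cohort as the reference for the primary rate ratios. Item 7 of Section 9.7.2.5 examines the first 6 months and lags of 12, 18, 24 and 48 months. It does not say how the comparator is handled.

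**The concern.** Section 8 gives the lag two purposes: to allow for induction and latency, and to deal with early cancer symptoms mistaken for dermatitis. The second applies to corticosteroids as well. Section 7.1 notes that undiagnosed CTCL may be treated as dermatitis, and Section 9.7.2.6 recognises possible reverse causation among corticosteroid users, but examines it only against untreated patients.

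If the window is removed from one side only, misdiagnosed early cancers leave the exposed rate and remain in the reference rate. Section 9.9 says that interpretation rests on the point estimate, the upper confidence limit and the absolute excess risk. All three would move in the falsely reassuring direction if early comparator rates are raised.

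The timing of the repair also matters. Each site adapts the core protocol (Section 9.1), computes its own person-time and passes on aggregated strata (Sections 9.7 and 9.7.1.4). Four sites could resolve Sections 8 and 9.3.4.6 differently. The coordinating center could not remove months 0-6 afterwards unless the sites had tabulated them separately.

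**Working it through.** **Step 1. Is the lag really removed from tacrolimus person-time?** Inputs are the follow-up distributions in Tables 5 and 6 and the person-years in Table 3, which are stated to account for the 6-month induction period. Take the sum of (users in band × band midpoint) and subtract 0.5 year per user.

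| | Users (Tables 5, 6) | Midpoint person-years | Less 0.5 year each | Result | Table 3 |
|---|---|---|---|---|---|
| Adults | 103,175 | 602,953.5 | 51,587.5 | 551,366 | 551,369 |
| Children | 25,479 | 146,020.5 | 12,739.5 | 133,281 | 133,285 |

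Both reproduce to within 4 person-years. The planned tacrolimus person-time is therefore net of the lag. No corresponding comparator figure is given.

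**Step 2. Share of person-time in months 0-6.** Mean unlagged follow-up is 602,953.5/103,175 = 5.84 years (adults) and 146,020.5/25,479 = 5.73 years (children). The share is

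- adults: f = 51,587.5/602,953.5 = 0.0856
- children: f = 12,739.5/146,020.5 = 0.0872

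Applying f to the corticosteroid cohort assumes that its follow-up resembles that of tacrolimus users.

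**Step 3. Effect on the rate ratio.** Let λ be the corticosteroid event rate after month 6 and kλ the rate in months 0-6. The unlagged reference rate is f·kλ + (1 − f)·λ = λ[1 + f(k − 1)]. The rate ratio is therefore multiplied by 1/[1 + f(k − 1)]. This takes f and k as equal across strata. The value of k is not in the documents and is an assumption throughout.

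| k | Adults | Children |
|---|---|---|
| 1 | 1.00 | 1.00 |
| 2 | 1/1.0856 = 0.92 | 1/1.0872 = 0.92 |
| 3 | 1/1.1711 = 0.85 | 1/1.1745 = 0.85 |
| 5 | 1/1.3422 = 0.75 | 1/1.3490 = 0.74 |

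Below k = 1 the direction reverses: at k = 0.5 the adult factor is 1/(1 − 0.0428) = 1.04.

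**Step 4. Shorter comparator follow-up.** Phase I averages in Table 3 are 198,400/66,127 = 3.00 years (adults) and 50,316/19,948 = 2.52 years (children). If these are net of the lag (an assumption), f = 0.5/3.50 = 0.143 and 0.5/3.02 = 0.165. At k = 2 the factors become 0.88 and 0.86. The share, and hence any bias, grows if comparators are followed for less time.

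**Step 5. After the fix.** With the same window removed from both sides, the factor from this source is 1.00 by construction.

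**The case against.** The strongest reply is that Section 8 already sets the lag for the whole study, and the abstract speaks of the study cohorts before mentioning it. On that view 9.3.4.6 is loosely worded and a symmetric lag was always intended. This stands in part: one-sided lagging is a possible consequence of the text, not an established fact. But Section 8 does not cure 9.3.4.6. It counts from the start of treatment, whereas Key Definitions and Section 9.2.3.2 allow past and prevalent corticosteroid users, whose treatment may have begun before cohort entry. Only a rule tied to the start date can be programmed uniformly. Figure 5, the worked example for this cohort, was not available for this check. A lag drawn there would add to the conflict with the text of 9.3.4.6, not remove it.

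Three stronger inferences are tempting, and the documents do not support them:

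- **That the study cited in Section 7.1 supplies k.** Its relative risks of 3.8 (under 30 days of use) and 14.8 (1-6 months) compare use with nonuse, by duration of use, for lymphomas with skin involvement. The later categories are 25.8, 12.9 and 82.9. Early-to-later ratios from the list are 3.8/25.8 = 0.15, 14.8/25.8 = 0.57, 14.8/12.9 = 1.15 and 14.8/82.9 = 0.18, so three of these four are below 1. Duration of use is also not time since cohort entry. The list does not settle k in either direction.
- **That 9.3.4.7 is a separate error.** As written, corticosteroid and untreated patients both count from the same assigned start date, so the secondary comparison is symmetric.
- **That early death or disenrolment adds bias.** Such patients contribute both their events and their time to a person-time rate, and no further mechanism is shown.

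It also stands that comparators without a recorded atopic dermatitis diagnosis enter only after another prescription in the prior 12 months, which may blunt any early peak.

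**Conclusion.** The concern holds as an internal contradiction that affects the primary estimate if resolved the wrong way. Sections 9.3.4 to 9.3.4.4 lag the exposed cohorts, 9.3.4.6 does not lag the comparator, and Section 8 leaves the matter open. Programmed as written, 9.3.4.6 biases the primary rate ratio downward when k exceeds 1. There is no bias at k = 1, about an 8% reduction at k = 2, 15% at k = 3 and about 25% at k = 5. These figures rest on an assumed k and on comparator follow-up resembling tacrolimus follow-up. CTCL and other lymphomas are the endpoints of most concern because the protocol itself describes the protopathic mechanism for them.

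A reader might infer that the lag analyses in sensitivity item 7 share the asymmetry. The protocol does not say so, but neither does it say that comparators are lagged there, so item 7 cannot be relied on as a safeguard.

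**What to change.** Reconcile Sections 8 and 9.3.4.6 before sites extract data:

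1. In 9.3.4.6, state that corticosteroid time at risk and events count from 6 months after the start date, parallel to 9.3.4.1. Use the start date as the anchor in Section 8 as well, so that past and prevalent users are handled in the same way at every site.
2. In item 7 of 9.7.2.5, state that each alternative lag, and the months 0-6 window, applies to the corticosteroid comparator as well as to the exposed cohorts.
3. As a consequence of the first change only, apply the same start-date lag to the untreated cohort in 9.3.4.7, so that the secondary comparison stays symmetric.

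The cost is a few sentences, minor code changes at each site and about 9% of comparator person-time. If symmetric lagging was always intended, this is a clarification. If it was not, it removes a possible bias from the primary rate ratio.

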9.3.4.7 Untreated Cohort

Person-time will be accumulated from the start date (see Section 9.2.3.3) to the earliest of the following dates: prescription for moderate- to high-potency topical corticosteroids, prescription for topical tacrolimus, prescription for topical pimecrolimus, or end of follow-up (Figure 6).

Figure 6. Exposure Assessment: Example for Patients Contributing Person-time to the Untreated Cohort and Any Other Cohort

9.3.5 Endpoints

Incident malignancies are defined as the first occurrence of one of the malignancies of interest occurring in study patients during study follow-up. If a person develops more than one primary malignancy of interest (i.e., a malignant melanoma and a lymphoma), only the first malignancy will be included and counted as an individual record. In a sensitivity analysis, the occurrence of each endpoint will be evaluated regardless of a prior occurrence of any of the other study endpoints during the study period.

The third version of the International Classification of Diseases for Oncology (ICD-O-3), which provides site (topography) and histology (morphology) codes for neoplasms, will be used to define malignancies in the study. The ICD-O-3 topography code C44 (skin) will be used together with the corresponding morphology codes to identify malignant melanomas (MM) and non-melanoma skin cancers (NMSC). The complete lists of ICD-O-3 codes for the malignancies of interest are presented in Annex 4.

The following incident malignancies will be included in the study.

Skin Malignancies

- Malignant melanoma, including in situ carcinomas (MM)
- Non-melanoma skin cancer (NMSC), including in situ carcinomas (i.e., squamous cell and basal cell carcinomas, Merkel cell carcinoma, and adnexal and skin appendages neoplasms)

Skin malignancies will be evaluated as a group (“Any skin malignancy”) and by individual malignancy type—i.e., melanoma, NMSC. In a sensitivity analysis, NMSC will be further subclassified as basal cell carcinoma and squamous cell carcinoma.

Lymphomas

- Cutaneous T-cell lymphomas (CTCL)
- Hodgkin lymphomas (HL)
- Non-Hodgkin lymphomas (excluding CTCL)

Lymphomas will be analyzed as a group (“Any lymphoma”) and by specific lymphoma type—cutaneous T-cell lymphoma, Hodgkin lymphoma, and non-Hodgkin lymphoma (excluding CTCL). In a sensitivity analysis, lymphomas will be grouped as cutaneous or noncutaneous lymphomas.

The classification of lymphomas has undergone several revisions during the last decade, and the most recent revised classification published by the World Health Organization (WHO) in 2008 represents a worldwide consensus on the diagnosis of these tumors [13]. A variety of T-cell and B-cell neoplasms can involve the skin, either primarily or secondarily. The term “primary cutaneous lymphoma” refers to CTCLs and cutaneous B-cell lymphomas (CBCLs) that either frequently present first in the skin (before there is evidence of systemic disease) or commonly involve the skin relatively early in their natural history. Because primary cutaneous lymphomas are clinically distinct from other lymphomas (which involve skin only uncommonly or only in patients with advanced disease) and may require distinct approaches to treatment, recent classification systems for non-Hodgkin lymphomas such as the European Organisation for Research and Treatment of Cancer (EORTC) classification for primary cutaneous lymphomas and the WHO 2008 classification for tumors of hematopoietic and lymphoid tissues included primary cutaneous lymphomas as a distinct category [13,14]. However, the ICD-O-3 classification, which was published in 2001, does not incorporate these recent revisions to the classification of lymphomas.

Aiming to have the most up-to-date, standardized approach that incorporates as much as possible the recent changes in the classification of malignant cutaneous lymphomas and that can be implemented across all databases, we reviewed the ICD-O-3 codes for cutaneous lymphomas under “Mature T- and NK-cell Lymphomas” against the WHO 2008 classification for cutaneous lymphomas under “Mature T-cell and NK-cell Neoplasms” and

selected the ICD-O-3 codes that matched the definition and codes of cutaneous lymphomas in the WHO 2008 classification (see Annex 4, Table A4-3). This approach did not pose any problem for the identification of CTCLs. However, the identification of CBCLs (classified as a separate entity in WHO 2008) was not possible as the WHO 2008 codes for these tumors do not have correspondence in ICD-O-3. Therefore CBCLs (which occur considerably less frequently than CTCLs) will not be included within the cutaneous lymphomas group in this study although they are still expected to be identified as non-Hodgkin lymphomas in the study databases and would count toward that endpoint. Moreover, certain other rare lymphomas that were newly included with provisional codes in the WHO 2008 classification (and which are proposed for inclusion in the next edition of ICD-O), for example, primary cutaneous gamma-delta T-cell lymphoma, will not be explicitly included in this study. However, such lymphomas, if any occur in the study population and are coded less specifically, would be included in the non-Hodgkin lymphoma endpoint.

9.3.6 Case Identification and Validation

Potential cases of the targeted malignancies will be identified in PHARMO, Denmark, and Sweden using the list of ICD-O-3 codes shown in Annex 4. The development of a case validation approach will depend on whether validation of cases of neoplasms had been performed as part of the standard validation procedures by the data source from which cases originate (e.g., cancer registries, pathology registries, electronic medical records). Cases that are identified and recorded in the cancer registries will not require further validation because of the standard validation procedures used by the cancer registries

In, Denmark, and Sweden, cases will be identified through cancer registries and will not require validation [15].

In PHARMO, as in Phase I, cases will be identified in the pathology database (PALGA), which is mapped to the ICD-O-3 classification. Cases identified will be validated by an independent pathologist by reviewing the pathology excerpts of all pediatric cases, a random sample of adult cases, and all cases of CTCL. Staging information is not directly available in PALGA. In order to conduct the sensitivity analysis to assess surveillance bias (Section 9.7.2.5), staging information will be obtained from the Netherlands Cancer Registry (NCR). The sensitivity analysis will include all malignant melanoma cases identified in PALGA for which data from the NCR are available. Data from the NCR are currently available through 2014 and might be available through 2015 in 2018.

In the CPRD, for practices linked to the cancer registry, cases will be identified using ICD-10 codes. For practices not linked to the cancer registry, cases will be identified through the CPRD records and linkage to Hospital Episode Statistics (HES) data. The linkage of CPRD data to cancer registry data will be performed in the study. Note that the linkage is partial, and there is a lag of 2 years for obtaining data from the cancer registry. Cases from linked practices for which cancer registry information is not available will be identified through CPRD records and HES, as for practices not linked to the cancer registry. The ICD-O-3 coding system is not used for coding neoplasms in the CPRD. Therefore, the standard reference medical terminology or diagnostic coding systems used in the database (Read/OXMIS) will be mapped to the ICD-O-3 topography and morphology codes for each endpoint. CTCLs will be identified using the selected ICD-O-3 codes that matched the definition and codes of cutaneous lymphomas in the WHO 2008 classification of lymphomas as described in Section 9.3.5. For cases identified

through the CPRD or the Hospital Episodes Statistics linkage, validation of all pediatric cases, a random sample of adult cases of melanoma skin cancers and lymphomas (number of cases to be determined based on the final number of cases identified), and all cases of non-melanoma skin cancer and CTCL will be performed by reviewing the computerized information.

